# **1. Report of Prior Investigations**

## **1.1 Introduction**

A vascular aneurysm is a permanent, localized dilatation of a blood vessel at least 1 1/2 to 2 times the normal vessel diameter. The aorta is the most frequent site for aneurysms, with approximately 10% of aortic aneurysms located above the renal arteries in the thoracic segment. (Coselli and LeMaire, 1995.) Thoracic aortic aneurysms (TAAs) are less common than abdominal aortic aneurysms, however, detection of TAAs is increasing, perhaps due to an aging population, increased diagnostic capability or an increase in prevalence. (Mitchell, Miller and Dake, 1997.) Ascending and transverse arch aneurysms each comprise 25% of TAAs; the remaining 50% occur in the descending thoracic aorta. The most common cause of TAA is medial degenerative disease of the aortic wall, responsible for most ascending aortic aneurysms and most fusiform aneurysms involving the descending aorta. Arteriosclerosis, commonly found superimposed on aneurysmal disease of other etiologies, frequently results in saccular aneurysms. Additional causes of TAA are dissection, aortitis, trauma, and infection. (Coselli and LeMaire, 1995.) In cases of aortic dissection, which typically involves the descending thoracic aorta, the origin of the dissection is in the proximal descending aorta in about 25% of the cases. Traumatic TAA is typically caused by blunt chest trauma that produces partial aortic disruption. (Coselli, Buket and Crawford, 1996.)

Untreated thoracic aneurysms can be life-threatening. As many as 78% of untreated patients with TAA die within 5 years after diagnosis, most often from

rupture of the aneurysm. (Pressler and McNamara, 1980.) Conventional surgical treatment, either tube graft replacement or patch aortoplasty, is a high-risk surgical procedure. Repair of the descending thoracic aorta is performed with a thoracotomy and cross-clamping of the aorta, with or without a shunt by-pass to maintain distal perfusion. Cardiopulmonary bypass is used to control rising blood pressure. (Najafi, 1994.) Mortality associated with surgical repair of the thoracic aorta ranges from 12% to more than 50%, depending on the urgency of the procedure, coexisting debilitating diseases or conditions, and the patient's general health. (Moreno-Cabral, Miller, Mitchell, et al, 1984.)

As an alternative to conventional surgery, a less invasive endovascular procedure has been developed that may be used to treat certain aneurysms. A collapsed stent-graft, a metal stent coupled with a fabric graft, is introduced into the vasculature, advanced to the site of the aneurysm, and deployed to span the aneurysm. The device creates a new aortic lumen, excluding the aneurysm sac from blood flow while maintaining flow within the stent-graft, this less invasive technique is designed to prevent or decrease the need for open surgery, to reduce the need for blood transfusions, to decrease the use of anesthetics and other drugs, and to speed recovery time. A reduction in intensive care and total hospital stay should result, leading to an increased quality of life following the procedure and a reduction in cost.

Experience in the endovascular treatment of thoracic aneurysms is limited. Miller, et al, have published results from a series of 108 patients with descending TAA treated with a (homemade) endoluminal stent-graft. (Mitchell, Miller and Dake, 1997; Dake, Miller, Semba al, 1994; Skeens and Dake, 1997.) Atherosclerotic,

anastomotic, and post-traumatic true or false aneurysms and aortic dissections were treated. Complete aneurysm thrombosis and technical success was achieved in 103 of the 108 patients. There were 10 deaths (9.25%) patients experienced perioperative strokes, and there were 4 cases of paraplegia. During an average follow-up of 21.8 months (range 1 to 57 months), there were 2 documented cases of stent-graft failure and 5 late deaths (more than 30 days post operative). (Skeens and Dake, 1997.)

More recently, Nienaber et al prospectively evaluated the safety and efficacy of elective transluminal endovascular stent-graft implantation in twelve (12) consecutive patients with descending (Type B) aortic dissection and compared the results with conventional surgical repair in twelve (12) matched surgical control patients (Nienaber, 1999). Stent-graft treatment resulted in no morbidity or mortality, whereas surgery for Type B dissection was associated with four deaths (33%,  $p = 0.09$ ) and five serious adverse events (42%,  $p = 0.04$ ) within twelve (12) months. Stent-graft implantation was successful in all patients, with no endoleaks. There were no deaths or instances of paraplegia, stroke, embolization, side branch occlusion, or infection in the stent-graft group; nine patients had postimplantation syndrome, with transient elevation of C-reactive protein levels and body temperature as well as mild leukocytosis. All patients who received stent grafts recovered, as did seven (7) patients who underwent surgery for Type B dissection (58%,  $p = 0.04$ ). The authors conclude that these preliminary results suggest that elective, non-surgical implantation of a stent-graft is safe and effective in selected patients who have thoracic aortic dissection and for whom surgery is indicated. Compared to standard surgical repair, this study supports the clinical utility of the stent-graft for the treatment of thoracic aortic dissection. The first-generation Medtronic/Talent stent-graft has been investigated in a US DE Phase I pilot study involving 20 high-risk surgical candidates. The clinical study

described in this protocol is a study involving the second-generation Medtronic/Talent system. Compared to the first-generation stent-graft, the Medtronic/Talent endoluminal spring stent-graft system also features an enhanced delivery system, which is designed to facilitate insertion and negotiation through tortuous and calcified vasculature. The first and second-generation devices are identical in every way except for the differences in graft material thickness and the presence of the system's new delivery system. The delivery system features a flexible tapered tip as well, as a flexible stainless-steel coil at the delivery-system catheter's tip, both of which facilitate negotiation through tortuous vessels and reduce the potential for device kinking.

Since 1998, Harbor UCLA has treated 31 thoracic aortic lesions with the Medtronic Aneurx device, all of which have been part of commercial manufacturer DEs. A published review of 26 of these patients who were significant risks for surgical repair and who were implanted with the Aneurx thoracic stent-graft showed that 25 were treated successfully with no surgical conversions. Moreover, there was an overall decreased incidence of morbidity and mortality. (White, et al, 2001.)

An additional 14 subjects were treated with the Medtronic/Talent thoracic device and 1 Gore device between June 1998 and January 2002, either on a compassionate or emergency basis. In our experience, the Talent device has been particularly useful for patients with descending aortic aneurysms and dissections with the only limitation being adequate access for the 22 to 27 French delivery catheters.

## **1.2 Device Description**

This study will utilize the most advanced generation Medtronic/Talent system including the enhanced delivery system. The information needed for the use of this device is available in Medtronic's DE G980116. (Please refer to the letter from Medtronic Inc. dated December 19, 2001 (Attachment A) granting the investigator permission to reference the IDE number.) The use of this device in this study will be for the same aneurysm morphology as described in the reference .

## **2. Investigational Plan**

### **2.1 Purpose**

#### **2.1.1 Name and Intended Use of the Device**

The Medtronic/Talent Stent-Graft System is a flexible, implantable vascular stent graft endoluminal device preloaded in a delivery system that is used to exclude

thoracic aortic lesions (thoracic aneurysms, thoracic dissections, penetrating ulcers, traumatic transections and both traumatic and degenerative pseudoaneurysms).

The devices and intended use are described in IDE # G980116.

### **2.1.2 Objectives of the Investigation**

Both high risk and low risk patients with thoracic aortic lesions will be enrolled and treated. This includes patients with true thoracic aortic aneurysms (i.e., all layers of the vessel are affected; generally, of atherosclerotic origins, thoracic dissections, penetrating ulcers, traumatic transections and traumatic and degenerative pseudoaneurysms).

The primary objective of this investigational plan is to determine the safety of the Medtronic/Talent device when used to exclude thoracic lesions: true descending thoracic aortic aneurysms, dissections, penetrating ulcers, traumatic transections and traumatic and degenerative pseudoaneurysms from blood flow in high risk and low risk patients who are candidates for endoluminal repair.

### **2.1.3 Duration of the Investigation**

Accrual of study subjects will occur over approximately 3 years with all 50 subjects to be followed according to the Lifeline Registry of Endovascular Repair protocol for the life of the patient (Please see Attach C for the protocol).

---

## **2.2 Protocol**

This study-will be conducted with high risk and low risk patients who are considered suitable candidates for endoluminal repair of descending thoracic aortic lesions

including those with true aneurysms, aortic dissections, penetrating aortic ulcers, traumatic transections and pseudoaneurysms (both traumatic and degenerative). Adult male and female patients who fulfill the inclusion/exclusion criteria listed below, are eligible for enrollment.

### **2.2.1 Inclusion Criteria**

Subjects who participate in this study as study patients must fulfill the following criteria:

- Subject is  $\geq 18$  years of age.

- Subject is not pregnant or lactating. Females of child-bearing potential must practice a reliable method of contraception.
- Subject is diagnosed with one of the following conditions of the descending thoracic aorta. All conditions must be verified by diagnostic imaging [ultrasonography, computed tomography (CT), magnetic resonance (MRI) or angiography].
  - a true (i.e., atherosclerotic) supraceliac aneurysm (fusiform or saccular type) with or without a co-existing aortic dissection or penetrating aortic ulcer,
    - aortic dissection of DeBakey Type I or (Stanford A, proximal) in the absence of an aneurysm; or
  - penetrating aortic ulcer in the absence of an aneurysm; or
  - traumatic transection; or
  - pseudoaneurysm — traumatic or degenerative (i.e., one that does not involve all layers of the vessel and is not atherosclerotic in origin.
- Subject's anatomy is suitable for placement of the Medtronic/Talent Stent-Graff, with a distinct proximal aneurysm neck of 10 mm or more in length and a distal aneurysm neck of at least 10 mm.

- Subject has a TAA that is dilated to  $\geq 5$  cm in diameter,  $\geq 1.5$  times the diameter of the adjacent native/non-aneurysmal aorta or is symptomatic.
- Subject has a proximal and distal aortic neck diameter  $\geq 18$  mm and  $\leq 42$  mm.
- Subject has an arterial access site, either peripherally or via infrarenal abdominal aorta that is adequate for introduction of the stent-graft delivery system..
- Subject is competent to give informed consent.
- Subject will be available for the periodic follow-up (surveillance) after the procedure.

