#### **2.2.5.3.1 Proper-sizing of stent-graft**

For proper sizing of the Medtronic/Talent Endoluminal Stent-Graft, the information listed below must be measured and recorded on the TAA Worksheet CRF:

- diameter of the proximal aortic neck.
  - diameter of the aneurysm.
- diameter of the distal aortic neck; landing zone.
  - length of the posterior proximal aortic neck, from the proximal end of the aneurysm to the left subclavian artery, along the outer curve of the aorta.

- length of the anterior proximal neck, from the proximal end of the aneurysm to the left subclavian artery, along the inner curve of the aorta.
- aneurysm length: area of the aorta to be excluded by graft.
- length of the distal aortic neck, from the distal end of the aneurysm to the celiac trunk.
  - desired length of graft coverage.
  - access artery diameters
- sketch/tracing of aneurysm, penetrating ulcer, dissection

The condition of the arteries that will be used to access the descending aorta must also be assessed and documented to determine if access to the aneurysm can be achieved with the Medtronic/Talent Stent-Graft System. Vessel diameter, tortuosity, stenosis, plaque, etc., will affect the ease of insertion.

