### **2.3.4 Patient population**

The patients who will be enrolled in this study will have documented descending thoracic aneurysms, dissecting aneurysms, penetrating ulcers, traumatic transections and pseudoaneurysms (traumatic or degenerative). People at risk for TAA are predominantly elderly (over 65), either male or female, of all ethnic backgrounds. The study will include high risk and low risk males and females between 18 and 90 years of age, of any race who have been diagnosed with supraceliac lesions of the descending thoracic aorta including true aneurysms, dissecting aneurysms, penetrating ulcers, traumatic transections or traumatic or degenerative pseudoaneurysms, who are considered to be good candidates for endoluminal repair of the aneurysm, and whose vascular anatomy fulfills the requirements for Medtronic/Talent Endoluminal Stent-Graft implantation.

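### The only inclusion bullet for dissection without aneurysm is labelled Stanford A, proximal, which conflicts with its own descending-aorta heading and leaves isolated Type B dissection without a diagnosis bullet

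*Protocol*

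**What the plan says.** All references are to the Protocol.

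- **Section 2.2.1, list heading:** "Subject is diagnosed with one of the following conditions of the descending thoracic aorta". Five diagnosis bullets follow: true aneurysm, dissection, penetrating ulcer, traumatic transection and pseudoaneurysm.
- **Section 2.2.1, dissection bullet:** "aortic dissection of DeBakey Type I or (Stanford A, proximal) in the absence of an aneurysm; or".
- **Section 2.2.1, first bullet:** a true "supraceliac aneurysm (fusiform or saccular type) with or without a co-existing aortic dissection or penetrating aortic ulcer". This is the only other way in for a patient with a dissection, and it does not restrict the dissection's class.
- **Section 2.2.1, later criteria:** these apply to every subject. They ask for distinct proximal and distal aneurysm necks of at least 10 mm, and for a thoracic aortic aneurysm that is dilated or symptomatic.
- **Section 2.2:** the study is in "suitable candidates for endoluminal repair of descending thoracic aortic lesions", with aortic dissections named among them.
- **Section 2.3.4:** subjects are those "diagnosed with supraceliac lesions of the descending thoracic aorta including true aneurysms, dissecting aneurysms, penetrating ulcers" and other lesions.
- **Section 2.1.2:** the primary safety objective covers exclusion of "true descending thoracic aortic aneurysms, dissections, penetrating ulcers, traumatic transections and traumatic and degenerative pseudoaneurysms from blood flow".
- **Section 1.1:** the one study cited specifically on dissection enrolled "consecutive patients with descending (Type B) aortic dissection and compared the results" with matched surgical controls.

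**The concern.** The dissection bullet and the heading over it point to different parts of the aorta. The heading, sections 2.2 and 2.3.4 and the cited dissection study all point to the descending aorta. The bullet's own qualifier points to proximal, Stanford A disease.

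Dissection is one of the lesion types named in the primary safety objective, so this bullet helps to decide whose outcomes answer that objective. An investigator who follows the bullet turns away an isolated Type B dissection and may accept a proximal one. An investigator who follows the heading does the reverse and departs from the written criterion. Either way, the dissection-without-aneurysm group would not be defined by one consistent rule, and its safety results would be hard to attribute to a stated population.

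**Working it through.** No arithmetic applies: the protocol attaches no rate, power or sample-size figure to this criterion. The check takes three kinds of patient through the text of 2.2.1.

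**1. Isolated descending (Type B) dissection, no aneurysm.**
- True aneurysm bullet: not met, because there is no aneurysm.
- Dissection bullet: not met, because the classes named are DeBakey Type I and Stanford A, proximal.
- Ulcer, transection and pseudoaneurysm bullets: not met, because they are different diagnoses.
- Result: 0 of 5 bullets met. The heading requires a descending location, but it does not add a class that the bullets omit.

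**2. Proximal (Stanford A) dissection, no aneurysm.**
- Dissection bullet: met.
- Heading: in conflict for disease confined to the proximal aorta. If a proximal dissection also involves the descending aorta, the heading might be satisfied, but case 1 is still left out.
- Section 2.2.2: no exclusion criterion names a dissection class, so nothing there removes this patient on class.

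**3. Descending dissection with a co-existing true aneurysm.**
- True aneurysm bullet: met, whatever the dissection class. This patient is eligible on diagnosis.

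**The damaged wording.** The bullet has an or with nothing between it and the parenthesis, so a type label may be missing. There are two possibilities:
- The lost label fits Stanford A, proximal. The bullet is then proximal only, and conflicts with the heading.
- The lost label names a distal class. The bullet then contradicts its own parenthesis.

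Neither makes the text consistent.

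**The later criteria.** Cases 1 and 2 have no aneurysm. Read just as literally, both fail the requirements for a thoracic aneurysm and for aneurysm necks. The same holds for the ulcer bullet, which also specifies no aneurysm, and for a transection without one. So correcting the class label alone would not give any no-aneurysm diagnosis a clear route in.

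**What happens to a misclassified patient.** Section 2.2.3 says that if new information after implant shows a patient does not meet the criteria, that patient is followed for safety but left out of the final analysis. The rule could therefore reach case 1, but only when ineligibility comes to light in that way.

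**Size.** One of the five diagnosis bullets is affected. Planned enrolment is 50 (section 2.1.3). No split by diagnosis is given, so the number affected could be 0 and has no stated upper limit short of the number enrolled with dissection and no aneurysm.

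**The case against.** The strongest reply is that the key phrase is visibly damaged. The text contains many reading errors, and short tokens such as I and A are easily lost or misread. Section 1.1 also speaks of dissections that originate in the proximal part of the descending aorta, so the word proximal does not by itself mean the ascending aorta. This is a good reason to check the source before amending. It does not remove the conflict, because the parenthesis as it stands pairs proximal with Stanford A.

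Several stronger readings are tempting, and the documents do not support them:

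- *The trial cannot report safety in descending dissection.* It can, for dissection with a co-existing true aneurysm. The gap concerns dissection without aneurysm.
- *The primary objective is restricted to descending dissection.* In 2.1.2 the word descending is attached to the aneurysms, and the dissections are unqualified. The descending scope comes from 2.2, the heading in 2.2.1 and 2.3.4. Even 2.3.4 speaks of dissecting aneurysms.
- *The sizing section settles the matter.* It measures "from the proximal end of the aneurysm to the left subclavian artery, along the outer curve of the aorta", which is worded for aneurysms and says little about dissection without one.
- *Any implanted Type B patient drops out of the analysis.* Section 2.2.3 depends on new information. Sections 2.2.5.1 and 2.2.5.2 require imaging before implantation, which would ordinarily show the dissection, so a patient enrolled knowingly is not clearly covered.
- *All 12 stent-graft patients in the cited study would be ineligible.* They had Type B dissection, but the protocol does not say whether any also had an aneurysm and so could use the first bullet.

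**Conclusion.** The point holds in a limited form. As written, 2.2.1 contradicts itself on which dissections without aneurysm may enter: the bullet is labelled Stanford A, proximal, under a descending-aorta heading, and sections 2.2 and 2.3.4 side with the heading. An isolated Type B dissection meets no diagnosis bullet. Separately, the criteria for an aneurysm and aneurysm necks do not fit the no-aneurysm diagnoses that the same list admits.

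The conclusion assumes that the parenthesis has been read correctly from the source and that eligibility is applied as listed, which section 2.2 requires. It does not depend on what stood after the or. The number of the 50 subjects affected is unknown, and no bias in any estimate can be calculated. The point still matters because the text decides who may enter, and in some circumstances who is analysed, for a lesion named in the primary objective.

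**What to change.** First check the source document for a label lost after the or in the dissection bullet. Then, in one amendment:

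- Reconcile the dissection bullet with the heading of its own list and with sections 2.2 and 2.3.4. If proximal dissection is intended, revise the heading and those sections instead.
- Reconcile the no-aneurysm diagnoses with the criteria that require a thoracic aneurysm and aneurysm necks, for example by stating to which diagnoses each anatomical criterion applies.

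Which dissection classes are eligible, and which anatomical limits apply to them, is for the sponsor to decide. The cost is a wording amendment to 2.2.1, and to the population sections if proximal dissection is intended. Reconciling the text does not by itself call for extra subjects, visits or procedures.

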### **2.2.2 Exclusion Criteria**

Subjects who would participate as study subjects and who fulfill any of the following criteria may not participate in this study:

- Subject has TAA with less than 10 mm proximal fixation length.
- Subject has an aneurysm that would require exclusion by the stent graft of the segment of the aorta that gives rise to dominant spinal cord/intercostal arteries.
- Subject has a lesion that prevents delivery or expansion of the device.
- Subject has systemic infection or is suspected of having systemic infection.
- Subject has a known mycotic aneurysm.

- Subject is not available or is not willing to come back for periodic follow-up (surveillance) after the procedure.

### **2.2.3 Withdrawal and Lost-to-Follow-up**

Patients may be withdrawn from the study for a number of reasons. The following is a summary of the possible reasons for withdrawal.

Subjects may voluntarily withdraw from the study. The reason for withdrawal must be documented on the Termination CRF (Attachment E).

After the implant procedure, some subjects may not return for follow-up visits. A minimum of three (3) attempts to contact such patients must be made. All attempts are to be documented on the Termination CRF.

Subsequent to enrollment, if new information demonstrates that a patient does not meet the inclusion/exclusion requirements, the patient must be withdrawn from the study. The reasons for withdrawal must be documented on the Termination CRF. If such information is not discovered until after the implant procedure, the patient will still be followed for safety reasons but will not be included in the final analysis.

In some cases, an implant procedure will be initiated (i.e., an attempt to pass or deploy the device) but is aborted prior to device deployment. Such patients maintain their enrollment status (since this is an intent-to-treat study) but need not

be followed. On the other hand, if a patient is initially screened and enrolled, but no procedure is ever initiated, the patient is cancelled and his/her enrollment position is made available to another patient.

Patients who are enrolled in the study group and are converted to surgery due to peri- or post-implantation complications will be followed for a minimum of 12 months after enrollment. Conversion to surgery is documented on the Procedure CRF.

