#### **2.2.4 Study Design**

This study is a prospective evaluation of patients receiving the investigational device to determine the proportion in whom successful implantation is achieved, as indicated by aneurysm exclusion and graft patency at implant, time of discharge, and 1-, 6-, and 12-months following implantation, and to determine the proportion of patients who experience adverse events during and after the implantation procedure, including comorbidities and overall mortality rates. The percentage of patients in whom technical and clinical success is achieved, and the percentage who experience serious adverse effects will be determined. Additional endpoints that will be evaluated are length of stay in intensive care following the procedure, total length of hospital stay and recovery time.

Patient data and follow-up information and images will be stored with the Lifeline Registry for Aneurysm Repair with periodic reports to the FDA up to the 5-year follow-up supplemented with reports from the Registry database.

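### Implanted patients later found ineligible are left out of the final analysis, against the protocol's own intent-to-treat statement and its primary safety objective

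*Protocol*

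**What the plan says.** Protocol section 2.2.3 sets a mandatory rule for patients already enrolled: "if new information demonstrates that a patient does not meet the inclusion/exclusion requirements, the patient must be withdrawn from the study". Where the discovery comes only after implantation, "the patient will still be followed for safety reasons but will not be included in the final analysis". No exception is made for the safety analysis.

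The following paragraph deals with procedures started but abandoned before the device is deployed: "Such patients maintain their enrollment status (since this is an intent-to-treat study) but need not" be followed. A patient in whom no procedure is ever started is cancelled and the place is reused.

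Section 2.1.2 gives the aim: "The primary objective of this investigational plan is to determine the safety of the Medtronic/Talent device". Section 2.2.4 describes a prospective evaluation of patients who receive the device. It asks for the proportion with adverse events, for overall mortality and for technical and clinical success, and adds that "the percentage who experience serious adverse effects will be determined". It does not restrict any of these to patients confirmed as eligible.

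**The concern.** The patients affected carry a permanent implant. Their events are collected and then left out of the final analysis of a study whose main question is whether the device is safe. A patient who never received a device keeps enrolled status on intent-to-treat grounds, while one who did receive it can be dropped.

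The second worry is how a patient comes to be found ineligible. The trigger is any new information after enrollment, with no time limit. Some exclusion criteria in section 2.2.2 can be called into question by a poor result:

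- "Subject has a lesion that prevents delivery or expansion of the device": failure to expand may become apparent only at deployment.
- "Subject has TAA with less than 10 mm proximal fixation length": a leak or migration invites a second reading of the neck.
- Coverage of the "segment of the aorta that gives rise to dominant spinal cord/intercostal arteries": section 2.2.6.4 lists paraparesis and paraplegia from lost spinal cord flow among the serious complications, and such an event would prompt review of this criterion.

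If those removed are mostly patients who did badly, the reported rates favour the device. That is the direction hypothesised in section 2.2.6.4, which expects fewer serious adverse events than with surgery. Even if removal is unrelated to outcome, the estimate no longer describes everyone exposed.

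**Working it through.** **Rules side by side**

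| Situation | Enrollment and analysis status (2.2.3) |
|---|---|
| No procedure started | Cancelled, place reused |
| Procedure started, device not deployed | Stays enrolled, on intent-to-treat grounds |
| Device implanted, later found ineligible | Withdrawn, followed for safety, left out of the final analysis |

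The third row cannot be squared with the second under one intent-to-treat principle. Nor does it fit section 2.2.4, because these patients did receive the device. The withdrawal sentence is also not made subordinate to the protection in the second row, so an aborted case later judged ineligible falls under both rules.

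**Is eligibility closed before implantation?** Largely, but not entirely. Sections 2.2.5.2 and 2.2.5.3.1 require neck lengths, diameters and access vessels to be measured and recorded beforehand. Section 2.2.3 nevertheless provides expressly for discovery afterwards, and nothing in the protocol limits that later judgement to the pre-procedure record.

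**Size (illustration)**

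The protocol gives 50 subjects (2.1.3) but no expected event rate and no expected number of late-found ineligible patients, so there is no planned figure to reproduce. Assumptions: all 50 are implanted, x have an event or failure, k are removed, and j of those k had the event.

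- Rate with everyone kept: x/50.
- Rate after removal: (x − j)/(50 − k).
- Exact (Clopper-Pearson) 95% limits for a events in n: the 0.025 quantile of Beta(a, n − a + 1) and the 0.975 quantile of Beta(a + 1, n − a). With a = 0 the lower limit is 0.

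| x | k removed | j with event | Rate | Exact 95% CI |
|---|---|---|---|---|
| 5 | 0 | – | 5/50 = 10.0% | 3.3 to 21.8 |
| 5 | 1 | 1 | 4/49 = 8.2% | 2.3 to 19.6 |
| 5 | 2 | 2 | 3/48 = 6.25% | 1.3 to 17.2 |
| 5 | 2 | 1 | 4/48 = 8.3% | 2.3 to 20.0 |
| 5 | 2 | 0 | 5/48 = 10.4% | 3.5 to 22.7 |
| 5 | 3 | 3 | 2/47 = 4.3% | 0.5 to 14.5 |
| 5 | 5 | 5 | 0/45 = 0% | 0 to 7.9 |
| 5 | 5 | 0 | 5/45 = 11.1% | 3.7 to 24.1 |
| 10 | 0 | – | 10/50 = 20.0% | 10.0 to 33.7 |
| 10 | 1 | 1 | 9/49 = 18.4% | 8.8 to 32.0 |
| 10 | 3 | 3 | 7/47 = 14.9% | 6.2 to 28.3 |

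**Removal unrelated to outcome.** Here j is hypergeometric with mean k·x/50. The expected rate is (x − k·x/50)/(50 − k) = (x/50)(50 − k)/(50 − k) = x/50. With x = 5 this is 10.0% for any k, so no bias is expected. The distortion comes only from removal that is linked to outcome.

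**The case against.** The best case for leaving the text alone has five parts.

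- **There are controls.** Section 2.2.5.2 has imaging results verified through Lifeline Registry mechanisms, and that registry protocol is an attachment not available here. New information must demonstrate ineligibility, and the reason goes on the Termination CRF. This stands to the extent that one cannot say independent review is absent. But the protocol text neither confines late decisions to pre-procedure data nor keeps the outcome from those deciding.
- **The events are not lost.** Adverse experiences are recorded on CRFs (2.2.6), and data go to the registry and into reports to the FDA (2.2.4, 2.2.5.6, 2.2.5.7). This is true, and the criticism should be confined to the final analysis. Those channels do not put the patients back into it.
- **The examples are uneven.** The spinal artery criterion concerns planned coverage, so paraplegia alone does not prove a breach. A re-read neck length is a re-read of a pre-procedure image. Delivery failures mostly fall under the aborted-case rule. This is fair, and it is why outcome-related removal is described as permitted and not as expected. A bad result can still prompt the re-reading.
- **The intent-to-treat phrase is a parenthesis about aborted cases.** It is not a full definition of an analysis set. The conflict with the safety objective does not depend on it.
- **A statistical analysis plan may define an all-treated safety set.** None is at hand. One that did so would contradict the protocol, which fixes the exclusion itself.

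**Conclusion.** The concern holds. As written, section 2.2.3 takes patients who received the device out of the final analysis of a single-arm study of 50 whose primary objective is the safety of that device. It contradicts the intent-to-treat reasoning one paragraph later.

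The size cannot be stated from the protocol. If all 50 are implanted and 5 have an event, removing one to three patients who all had events would turn 10.0% into 8.2% to 4.3%. Removing event-free patients would raise the rate slightly, and removal unrelated to outcome leaves it unchanged on average. Nothing in the protocol shows that outcome-related removal occurred. The defect is that the rule permits it and that the main estimate would not cover all exposed patients. It should be corrected, because it determines the analysis set for the primary objective.

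**What to change.** In section 2.2.3, replace the exclusion from the final analysis with a statement that every patient in whom a procedure was initiated is included in the primary safety and success analyses, whatever is later learned about eligibility. This is wider than implanted patients alone, and it matches the section's own treatment of aborted cases. State that the withdrawal sentence does not override it.

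Report late-found ineligibility as a protocol deviation, giving the criterion, the time of discovery and the patient's outcome. An eligible-only analysis may be kept as a sensitivity analysis, with ineligibility judged on pre-procedure data only.

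One reconciliation is needed alongside. Section 2.2.3 says patients aborted before deployment need not be followed, while section 2.2.6.2 has patients who are converted or only observed followed in the same way as the rest, with assessments at 1, 6 and 12 months. The two passages must be made to agree, because they decide what data exist for aborted cases.

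The cost is a short text change and that reconciliation. Implanted patients need no extra visits, since 2.2.3 already follows them. Any extra follow-up of aborted cases depends on how the two sections are reconciled. Reported rates may move in either direction, and will look less favourable only if the patients now kept did worse than the others.
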